The factors demonstrate predictive validity as children with ADHD were rated by teachers as significantly worse than students without ADHD and the measure correlated significantly with measures of academic achievement and academic efficiency, even with ADHD symptoms partialled out (DuPaul et al., 1991). Items are rated by teachers on a five-point Likert scale, and scores were summed for each of the two factors. Scores from 5-35 for the Academic Success factor ranged and from 5-60 for the Academic Productivity factor.

Secondary measure of distal academic achievement -- Wechsler Individual Achievement Test – III (Pearson, 2009). Participants will be administered the WIAT-III at the beginning and end of the study year to assess

academic achievement. This standardized, norm-referenced measure will take approximately 90 minutes to complete and has strong test-retest reliability ($r > .90$; Pearson, 2009) yielding composites of Total Reading, Basic Reading, Reading Comprehension and Fluency, Written Expression, Mathematics, and Math Fluency.

Social Validity (i.e., whether outcomes are acceptable, relevant, and useful)

Student-Teacher Relationship Scale (STRS; Birch & Ladd, 1998; Pianta, 1994, 1996, 1997; Pianta, Steinberg, & Rollins, 1995). To investigate differences in the student-teacher relationship, the STRS will be administered. The STRS a 28-item scale completed by the teacher. Teachers respond to items on a five point Likert scale ranging from 1 (Definitely does not apply) to 5 (Definitely applies). The STRS total score (coefficient alpha = .89; test-retest reliability over four weeks = .89) will be used as an index of the student-teacher relationship. The STRS also exhibits predictive validity (Pianta, 1996). Scores on the STRS range from 5-140.

Parent and Teacher Satisfaction. To obtain a measure of teacher and parent satisfaction with the intervention, and compare it to satisfaction in the SAU condition, raters will complete a measure of consumer satisfaction at the end of school. The measure used will be the satisfaction measure used with teachers and parents in the MTA study ([name] et al., under review). The measure may be divided into three factors: treatment satisfaction, perceived improvement, and demands of treatment. The internal consistency of the items on the parent factor were acceptable for the treatment satisfaction (coefficient alpha = .87), perceived improvement (coefficient alpha = .72), and demands of treatment (coefficient alpha = .84). On the parent version, test-retest correlations ranged from .42 to .62, representative of this type of measure.

Moderators

Grade. The grade of the children in the study will be used as a proxy for age. Students will be grouped as K-3 (primary) and 4-6 (secondary) for moderator analyses. The grade level moderator is important to investigate given clear evidence that effective behavior modification procedures decrease incrementally as children move up in grade (Brophy, 1986; [name] et al., 2002; White, 1975) and that more teachers are typically involved in working with the student at the intermediate/middle school level relative to the primary grade level.

Comorbidity. To investigate outcomes for disruptive behavior, the scores for ratings on ODD/CD symptoms will be used to identify the presence of comorbid Oppositional Defiant Disorder or Conduct Disorder. In the

Goal 2 study sample, the coefficient alpha for disruptive behavior disorder items from the DBD scale was .96. Comorbid disruptive behaviors were significantly improved in the Goal 2 study ([name] et al., 2010), making this a reasonable candidate for moderational analyses.

IEP Quality. IEP quality will be assessed using a composite rating by study investigators. Prior to quality ratings, IEPs will be de-identified to remove the participant name and information as well as any information about the school or district. Ratings will evaluate the alignment between needs listed in the IEP with goals/objectives stated in the IEP. This will be one way to determine the quality of the IEP document itself – well-written IEPs should have IEPs with close alignment between academic, behavior, and social/emotional needs and the goals to realize improvement (see appendix C for an outline of the coding sheet to be used in the present study; Pariseau, 2011). We will also track which goals are added by consultants to the DRC that were noted as needs by the teacher, but not listed on the IEP. The occurrence of these issues may indicate that the IEP is outdated, poorly constructed, or not reflective of current behavior. These indicators will comprise an IEP quality score investigated as a moderator. Specifically, the score will be calculated as: (Alignment between needs and goals + additional targets added)/overall alignment). A score of 1 would indicate perfect alignment whereas a score below 1 would indicate discrepancy between needs and goals.

Mediators

Three key components of the DRC intervention that are central to our logic model (see figure in the introduction) will be investigated as mediators of treatment outcome. It is expected that relative to the SAU group, the children in the DRC condition will experience a more positive classroom environment, receive more consistent feedback from teachers, and experience more consistent home-based consequences for school behavior. These three variables will each have a partial mediating effect, and the sum total will fully mediate the effect on treatment outcome.

Positive Student-Teacher Interactions. The ratio of positive to negative statements issued by the teacher on the SBTR observational measure will be used as an indicator of student-teacher interactions, with classrooms that have a positive environment having a larger number (i.e., more positives than negatives) relative to those that have a negative environment (i.e., fewer positives than negatives). Prior studies have demonstrated this information can be reliably collected (Vujnovic, et al., 2014). Further, these rates of positive to negative statements can be reliably modified based on background behavioral interventions such as the DRC ([name] et al., 2007). This measure will be collected across SAU and DRC groups.

Teacher Feedback for Targeted Behaviors. Observers in the DRC and SAU groups will have a list of the child's DRC/ITBC targets for each of their classroom observations. Observers will record the frequency of targeted behaviors exhibited as well as the number of targeted behaviors that receive appropriate feedback from the teacher. Observers will be blind to treatment condition. This approach to recording targeted behaviors and denoting which were responded to appropriately is part of the SBTR observation system developed by our group and used successfully in a number of school settings ([name] et al., 2010; [name] et al., 2007; Vujnovic, [name], et al., 2014). In this case we will modify the rule violations typically observed to be the individual child's targeted behaviors. The SBTR observation system has good inter-rater reliability: in one study the mean difference between the observers on total number of challenging behaviors was .53 (SD=3.3; Range=0-12). In an early childhood setting, agreement on the appropriate acknowledgement of challenging behavior was .68 ($p < .05$). For the total challenging behaviors variable, the correlation between the two observers was .94 ($p < .001$; [name] et al., 2010), supporting the inter-rater reliability of the observation measure. As a measure of validity, classroom challenging behaviors were negatively correlated with class climate $r = -.45$ (Massetti et al., 2007). The proportion of DRC/ITBC behaviors that were exhibited by the child that received feedback from the teacher will be used as an indicator of teacher monitoring and feedback of IEP goals.

Parent-Implemented Contingency Management. Families will be contacted in the morning and will be asked what contingencies were administered in the home the prior evening based on school behavior. For the SAU group, it is expected that the answer for most contacts will be none, unless the parent/school have arranged some contingency management program. For the DRC group, it is expected that the parent will report contingencies administered within the bounds of the DRC reward program. The number of days contingent rewards were accurately provided will be considered as a mediating variable. The collection of home reward related data suggested predictive validity in a recent meta-analysis (Vannest et al., 2010) and in our Goal 2 project. In the Goal 2 project, the percent of DRCs rewarded appropriately was negatively related to frequency of disruptive behavior at the end of the school year ($r = -.53$, $p = .002$; [name] et al., 2010). It is expected that the repeated morning phone calls will result in increased reliability for this measure. Teachers will also ask the child the next morning what reward was received and record this for the investigators. Teacher collected data should be less susceptible to reactivity for this variable than information provided by the parent.

Treatment Integrity and Fidelity of the Intervention as Implemented

Multiple methods will be used to document treatment integrity and fidelity. To record the integrity and fidelity (Cordray & Pion, 2006; Gresham, 1989; Lane, Beebe-Frankenberger, Lambros, & Pierson, 2001; Waltz, Addis, Koerner, & Jacobson, 1993) with which the DRC intervention is implemented, multiple procedures will be used that have been previously developed ([name], Greiner, & Gnagy, 1998; [name] et al., 2000). Treatment fidelity will be defined as the skill, care, and genuineness with which the intervention is implemented, and integrity will refer to the degree to which the intervention was implemented as intended.

Fidelity of Teacher Implemented Interventions. Observers will collect information each month (January to May) on teacher responses to student behavior and general classroom management techniques. These observations will include a recording of frequency counts of social reinforcement (e.g., praise statements) as well as commands and negative feedback (i.e., reprimands) directed toward the individual student across the entire school day. These frequency counts will be combined into a ratio of positive to negative statements and used as an indicator of classroom environment. After each observation, observers will also complete a post-observation inventory form. These forms will ask the observer to rate the teacher's use of social reinforcement, commands, tone of voice, and the overall classroom climate on a 7-point Likert scale. An example of this rating to be completed after the observation is in Appendix C.

Integrity of DRC/Targeted Behavior Feedback. Once per month, observers blind to treatment group assignment will spend a full school day in the child's classroom. The observer will be provided a copy of the child's DRC/ITBC and will record a frequency count of the occurrence of each targeted behavior. In addition, targeted behaviors for which the child received specific feedback from the teacher (i.e., were acknowledged; recorded on the DRC/tracking mechanism if appropriate) will also be recorded. This will yield a daily rate of target behavior occurrence, as well as the proportion of targeted behaviors that received appropriate feedback. Observers will also record the latency between the occurrence of a targeted behavior and teacher feedback regarding the behavior using a stop-watch (a decision rule of latency greater than 1 minute will be used to document "no response" to a target behavior).

For children in the DRC group, we will be able to obtain a sample of the proportion of DRC targets appropriately monitored by the teacher with feedback provided. The observer's completed DRC tracking sheet will also be compared to the DRC completed by the teacher to ascertain a sample of the accuracy of the report sent home to the parent each afternoon. This comparison will be made by the investigators/project coordinator to maintain observer blinds.

Integrity of Home Rewards for School Performance. Following each of the all-day school observations (i.e., monthly), SAU/DRC families will be

called/texted the next morning and the child and parent will be asked what contingencies were administered based on school behavior. In addition, teachers will be asked in the SAU and DRC groups about the provision of any school-based rewards. SAU

parents will also be asked whether they received any feedback from the teacher regarding the child's behavior in school that day and in what form (email, DRC, etc.).

In addition, for participants in the DRC group, parents will be asked each day to sign the DRC and record the reward administered, if any. Then, they will return the DRC to the teacher the next morning. This

will help promote home-school communication, and was a procedure used successfully in the Goal 2 project. It is hypothesized that the phone calls to query reward administration will replicate and extend these preliminary findings. Such phone calls have been successfully implemented by our lab on other funded projects (e.g., [name], et al., 2012; NIMH # R34MH078051). The interface between observations of primary outcome and observations of integrity/fidelity during the course of the study is illustrated above. Finally, parents/teachers in both groups will complete a checklist at post-treatment reporting how often they used the components of the DRC intervention (i.e., provided home reward; daily feedback).

Observations for Primary Outcome	Month	Observations for Integrity/Fidelity
SBTR Completed by Observer Blind to Condition (3 total)	January	Integrity/Fidelity Observation(1 total)
N/A	February	Integrity/Fidelity Observation(1 total)
N/A	March	Integrity/Fidelity Observation(1 total)
N/A	April	Integrity/Fidelity Observation(1 total)
SBTR Completed by Observer Blind to Condition (3 total)	May	Integrity/Fidelity Observation(1 total)

10.3 List any instruments or measurement tools used to collect data (e.g. questionnaire, interview guide, validated instrument, data collection form).

Include copies of these documents with your submission.

Response: See description in 10.2 above. In addition, a table of measures and administration schedule is included with the submission.

10.4 Describe any source records that will be used to collect data about subjects (e.g. school records, electronic medical records).

Response: N/A

*10.5 Indicate whether or not **individual** subject results, such as results of investigational diagnostic tests, genetic tests, or incidental findings will be shared with subjects or others (e.g., the subject's primary care physician) and if so, describe how these will be shared.*

Response: All subjects will have a diagnostic report generated following the intake/screening procedures sent to them for their clinical records. The report will be sent directly to the parents of the participant so that the parents can decide with whom to share it, if anyone.

*10.6 Indicate whether or not **study** results will be shared with subjects or others, and if so, describe how these will be shared.*

Response: At the end of the school year, all subjects will have a treatment summary report generated following the school year sent to them for their clinical records. The report will be sent directly to the parents of the participant so that the parents can decide with whom to share it, if anyone.

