2.0 Scientific Endpoints

2.1 Describe the scientific endpoint(s), the main result or occurrence under study.

*NOTE: Scientific endpoints are outcomes defined before the study begins to determine whether the objectives of the study have been met and to draw conclusions from the data. Include primary and secondary endpoints. Some example endpoints are: reduction of symptoms, improvement in quality of life, or survival. Your response should **not** be a date.*

Response:

Primary scientific endpoints are blinded observations of classroom behavior collected at the end of the school year and teacher ratings on the Disruptive Behavior Disorders Rating Scale, Impairment Rating Scale, Academic Performance Rating Scale, and BASC-2 rating scale. Teachers will also complete a rating of IEP goal attainment at the end of the school year.

Secondary outcome measures include assessments of academic achievement, classroom functioning, impairment, parent and teacher satisfaction with treatment, and student-teacher relationship.

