In the proposed study, the efficacy of the DRC as an enhancement to children with ADHD’s IEPs will be investigated in an experimental study. Children will be randomly assigned on the individual level to a condition where a behavioral consultant works with the child’s teacher(s) to construct a DRC, implement it, and monitor it, or to an IEP only, school as usual (SAU) condition, where teachers will attempt to meet the IEP goals and objectives as they typically would. A DRC is an operationalized list of target behaviors (e.g., “completes reading assignments with 80% accuracy or better,” “has no office time outs during the day”) that are evaluated each day by the teacher. The DRC is used as a means of providing the child and parent feedback on progress on a daily basis, and it doubles as a mechanism teachers can use to track and monitor the

child's behavior and progress on key functional domains. The DRC can be easily linked to IEP goals and objectives, providing a bridge between the IEP and the child's daily functioning in the classroom. Parents will also be taught in parenting meetings how to reward their child at home for successful attainment of DRC goals and how to communicate effectively with their child's teacher.

Measures of key outcomes will include observations of behavior in the classroom conducted by observers naïve to group assignment or study hypotheses, academic performance outcomes, parent and teacher ratings of functioning, and IEP goal attainment. Primary measures of outcome will be analyzed using ANCOVA procedures. Secondary measures will include teacher ratings of ADHD and disruptive behavior/impairment. Additional analyses will investigate moderators (grade level, comorbid aggressive behavior, IEP quality). It is further hypothesized that classroom environment and fidelity of implementation at school/home will mediate outcomes (i.e., classroom climate, the fidelity of teacher monitoring/feedback regarding behavior, consistency of parent-implemented consequences at home).

[figure not shown]
3.2 Include complete citations or references.

Response: Response: None included (see grant application for expanded background, preliminary studies, and references)

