The recruitment plan will aim for an equal number of subjects in the DRC and SAU groups, and participants will be block randomized across potential moderator variables including medication and grade level. In the Goal 2 study, for which these variables were unselected, 52% of the final sample was prescribed medication and 66% were in grades K-3 and 34% were in grades 4-6. Thus, it appears that the plan to have an equal number of subjects in each block is feasible with careful attention to recruiting participants in the older grades in the present application. Block randomization based on child psychoactive medication status will promote equal distribution of participants across this variable. The medication variable will be defined as “no medication” if the child is not prescribed psychoactive medication immediately prior to randomization and as “taking medication” if the child is prescribed psychoactive medication and it is being actively administered at the time of randomization. In sum, an equal number of participants (N=72/year) will be enrolled in four blocks each year (i.e., No medication/Primary grade; No medication/Intermediate grade; Taking medication/Primary grade; Taking medication/Intermediate grade). Random assignment will be conducted following the completion of all baseline measures by a blinded member of the study team ([name]). Following randomization, a form letter will be generated that informs the study staff and participating family of group

assignment. Consultants will then be randomly assigned to the case with an equal number of DRC and SAU cases assigned to each consultant.

For those students who are medicated with stimulant medication, we will ask parents to obtain permission from the child's doctor to withhold medication for the assessment days in January and May so as to collect information on the child's behavior when unmedicated.

Intervention Groups

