Impairment Rating Scale (Evans, Allen, Moore, & Strauss, 2005; [name] et al., 2006). The IRS is a rating scale that asks teachers to rate the severity of the child's problems and need for treatment and/or special services in important functional domains (i.e., relationship with peers, relationship with the teacher(s), academic progress, classroom functioning, self-esteem, overall need). There are six items on the scale, and scores on the measure range from zero (Not a problem/Definitely does not need treatment or special services) to six (Extreme problem/Definitely needs treatment or special services). Test-retest reliability estimates range from .60-.89 over a period of six months, and .54 to .76 over one-year. Ratings on the IRS predict mental health or school services, and there is evidence of convergent and discriminant validity on the measure ([name] et al., 2006). The average score for each of the individual domains rated will be used in the analysis; scores range from 0.0-6.0.

Rating of IEP Goals ([name], et al., 2010; Guy, 1976; [name] & Hoza, 1996; [name] et al., 2000). At each of the classroom observations, observers will be furnished with a copy of the child's DRC. In the case of the SAU group, an Individualized Target Behavior Checklist (ITBC) will be provided ([name] et al., 2010; [name] et al., 2005). The observer will complete this DRC/ITBC each day following the whole-day observation. In addition, the observer will ask teachers in the DRC group for a copy of the day's DRC and ask teachers in the SAU group to complete the same

ITBC. Therefore, we will have the teacher ratings of IEP goal attainment over the three days at baseline and endpoint with built-in procedures to assess inter-rater reliability.

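### Section 10.2 has the classroom observer make a request to the teacher that differs by arm, so at least one of the observer blinds the protocol claims cannot be kept

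*Combined protocol and SAP*

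**What the plan says.** The paragraph at issue is Rating of IEP Goals in section 10.2. It states: "At each of the classroom observations, observers will be furnished with a copy of the child's DRC". Children in school as usual (SAU) have an ITBC instead. It continues: "The observer will complete this DRC/ITBC each day following the whole-day observation". Then "the observer will ask teachers in the DRC group for a copy of the day's DRC and ask teachers in the SAU group to complete" that checklist. The stated product is teacher "ratings of IEP goal attainment over the three days at baseline and endpoint".

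Elsewhere the classroom observers are described as blind:

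- Section 2.1 defines the first primary endpoint as "blinded observations of classroom behavior collected at the end of the school year".
- Section 3.1 refers to "observers naïve to group assignment or study hypotheses".
- Section 10.2 repeats the blind for the SBTR, for the coding of teacher feedback on targeted behaviors, and for the monthly full-day integrity visits. The observation table attaches it to the SBTR column.
- The integrity paragraph of 10.2 gives the comparison of the observer's and the teacher's DRC to the investigators or project coordinator, expressly to protect the observers' blind.

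On timing, section 10.1 says: "Random assignment will be conducted following the completion of all baseline measures by a blinded member of the study team". After that, "a form letter will be generated that informs the study staff and participating family of group" assignment.

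**The concern.** Two different requests, one per arm, can be made correctly only by someone who knows the arm. Written into the observer's duties, this discloses allocation to people the plan calls blind. It also undercuts the safeguard in the integrity paragraph: the comparison of forms is kept away from the observer, but the collection of the teacher's form is not.

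The stake is highest if the exposed visits include the May SBTR. Classroom observation is the only outcome the protocol describes as blinded, and it is primary in sections 2.1, 10.2 and 17.1. Sections 2.1 and 17.1 accompany it on the primary list only with teacher ratings, and in the DRC arm the teacher delivers the intervention. The WIAT-III is not teacher-rated, but it is a secondary, distal measure and its assessor's blinding is not stated. If May scorers know the arm, the report loses its only blinded support for the behavioral result. The 20% double-coding and the cited inter-observer correlation of .96 would not reveal this, because they measure agreement, and two observers who both know the arm can share a leaning.

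**Working it through.** The plan gives no figure on this point. The check sets the text side by side and counts visits from the plan's own schedule.

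**1. Does the request need the arm?** Holding a target list need not reveal it, because section 10.1 says the ITBC was built in the same manner as a DRC. The request is different: one teacher is asked for a card already in use, the other to fill in a checklist. The observer must know which applies.

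**2. Which visits are meant?** Inputs: the SBTR and integrity paragraphs and the observation table, all in 10.2.

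| | Rating of IEP Goals | SBTR visits | Integrity visits |
|---|---|---|---|
| Length | whole day | 30 minutes | full school day |
| January | 3 days | 3 | 1 |
| February to April | not mentioned | 0 | 1 per month |
| May | 3 days | 3 | 1 |

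Per child the paragraph needs 3 + 3 = 6 whole days. The schedule offers 1 + 1 = 2 whole days in January and May, or 6 half-hour sessions (in May, 3 × 30 = 90 minutes). No scheduled visit is both whole-day and three per time point.

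**3. Which blind fails on each reading?** N = 216 (sections 5.1 and 29.3).

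- *SBTR days.* The blind in 2.1, 3.1, the SBTR paragraph and the table is broken in May. Sessions: 3 × 216 = 648 at most. If the request always comes after that day's scoring, the first session is clean. Then 2 × 216 = 432 are exposed when the same observer returns, and 0 when a different observer comes each day. Integrity days from February to April are not reached, because no such request has yet been made.
- *Whole-day integrity visits.* The blind in the integrity paragraph is broken, and so is the one for target-behavior feedback where its coding is done on those visits. Days from February to May: 4 × 216 = 864 of 5 × 216 = 1,080, again an upper bound. The January day is added only if it follows randomization, which is not stated. The May SBTR is exposed only if the same people score it. The SBTR paragraph calls the two sets of observations separate, but nothing says the observers are different people.

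**4. Can the baseline step occur?** Randomization follows all baseline measures (10.1). Consultants are assigned after it, and the DRC and the SAU goal list are built with them. At the baseline observation days there is therefore no arm to act on and no DRC to collect, so the arm-specific step cannot be carried out as written. For the same reason the January SBTR is not exposed.

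**The case against.** The strongest reply is that the paragraph describes the integrity visits. It speaks of a whole day, the integrity paragraph describes the same activity with the form in hand, and the SBTR paragraph mentions no DRC or ITBC. On that reading the primary outcome is not directly touched. This has weight, but it does not settle the matter. The three days at each time point match only the SBTR schedule, and the target-feedback paragraph makes target coding part of the SBTR system and supplies the list at each classroom observation. Even if the reply is right, the integrity blind still fails.

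A second reply is that the request follows scoring. The order of the text suggests this, and it is why 648 is a ceiling. The protocol requires neither that order nor a change of observer.

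A third is that section 10.3 refers to a schedule of measures submitted separately. It may identify the visits, but it would not change the wording of the request.

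Some stronger inferences should be resisted:

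- A reader might infer that every blinding statement is contradicted at once. The statements about the primary outcome are contradicted directly only on the SBTR-day reading.
- A reader might infer that two of the three Aim 3 mediators lose their blind on the whole-day reading. Only teacher feedback on targeted behaviors clearly does. The ratio of positive to negative statements is defined on the SBTR, and the monthly fidelity paragraph that also collects it claims no blind.
- A reader might infer a size of bias or a false-positive rate. The documents contain no estimate of observer leaning, so none is given.

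**Conclusion.** The contradiction stands. Rating of IEP Goals cannot be followed while every observer blind in the protocol is kept, and it must be corrected before the May observations can be reported as blinded. Confidence is high that at least one stated blind is contradicted. It is moderate that the May SBTR is exposed, because separate observers may be intended.

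The size is a count of visits, not of bias: up to 648 May SBTR sessions (432 or none under the timing conditions above), or up to 864 integrity days. The counts assume full enrollment of 216 and every scheduled visit made. The baseline step is unworkable on either reading.

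**What to change.** Reword Rating of IEP Goals so that the observer makes no arm-specific request, and reconcile it with the other paragraphs of 10.1 and 10.2:

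1. The teacher's DRC or ITBC goes to the project coordinator or investigators, who are already named for the comparison. It could be returned with the completed DRCs that section 17.3 already has collected as evidence of adherence.
2. Where observers need a target list, they use one identical, unlabelled form in both arms. Barring the list altogether would conflict with the target-feedback paragraph and lose the observer half of the inter-rater check.
3. State which visits the paragraph covers, and reconcile its baseline step with the timing of randomization and of DRC and goal-list construction in 10.1.
4. Do not send the allocation letter to observers. The protocol addresses it to study staff without saying whether observers are included.
5. Where existing staffing allows, a child's post-randomization integrity observer does not score that child's May SBTR.

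The cost is form redesign and some coordinator time for routing the teacher forms. Item 5 is conditional because the documents give no observer numbers. Sample size, endpoints and intervention do not change.

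These steps reduce unblinding but do not guarantee the blind. Integrity observers code whether a behavior was recorded on the DRC, and SBTR scorers code teacher consequences and praise, so either may infer the arm from seeing a DRC in use. Wherever the blind cannot be kept, the claim should be dropped.
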